Whether intervening on the complement system would slow the progression of mechanically/surgically induced osteoarthritis is not yet known in humans. In humans with advanced osteoarthritis undergoing total knee arthroplasty, elevated activity of the complement system has been established. Although the [name] lab has demonstrated increase activation of the complement system in early OA (Fig. below; Wang et al., 2011), whether meniscal tears are associated with activation of the complement system and alteration of gene expression in the synovial lining has not been previously investigated. Establishing whether this is the case with joint fluid aspiration and a synovial biopsy of patients undergoing arthroscopic meniscectomy for a degenerative meniscus tear, since they are believed to be patients with early osteoarthritis, will be a major step in further understanding the role of complement in the progression of osteoarthritis and potentially developing pharmacologic intervention strategies to slow osteoarthritis progression. This the focus of an exploratory aim of the proposed work.

Preliminary Studies and Current Status of the Field

Prospective Study on Arthroscopic Meniscectomy outcomes at the VA Palo Alto

We have performed a preliminary study on patients at the Palo Alto VA hospital undergoing arthroscopic meniscectomy (Mirza et al., 2011). In this study, we prospectively followed patients presenting to the orthopedic clinic with meniscus tears and who underwent arthroscopic meniscectomy. 78 subjects with a mean age of 51 years scheduled for knee arthroscopy for meniscal tears were enrolled. 45 subjects were available for final review at one year. History of acute injury within 6 months of surgery, Kellgren-Lawrence arthritis grade, and MRI appearance of meniscus tear (degenerative or not) was recorded for each patient. Pre- and one year postoperative WOMAC and WOMET were used to evaluate surgical outcome with statistical analysis done by ANOVA.

The Western Ontario and McMaster Universities Osteoarthritis Index (WOMAC) (Bellamy et al., 1988) and the more recent Western Ontario Meniscal Evaluation Tool (WOMET) (Kirkley et al., 2007) are self-administered validated outcome tools for osteoarthritis of the knee and meniscal tears of the knee.

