The psychometric properties of the WOMAC have been extensively studied in a number of publications. The original publication by Bellemy (Bellemy et al., 1988) found a high level of responsiveness, Chronbach's alpha greater than 0.85, acceptable validity testing against multiple other scales including the Lequesne, Bradburn, and Doyle, and superior efficiency over other measures.

The psychometric properties of the WOMET in a population of patients with degenerative meniscal tears were recently published (Sihvonen et al., 2012). Test-retest reliability 95% limits of agreement were 20.1 and -20.11 as a percentage of normal score. Cronbach alpha score for total WOMAC was 0.91 and was greater than 0.7 for all domains. Floor and ceiling effects were less than 30%. The WOMET was significantly correlated to the Lysholm knee score ($r=0.558$, $p<0.001$) and the 15-D scale ($r=0.311$, $p=0.002$). Construct validity and responsiveness were also established.

[figure not shown]
Preoperative baseline WOMET and WOMAC scores were compared to postoperative values at one year. Subjects were also defined according to age (greater than 50 or younger), BMI, OA grade (K-L classification), meniscal tear type (complex or simple), smoking history (yes/no), psychiatric diagnosis (yes/no), and PTSD diagnosis (yes/no). Two orthopaedic surgeons evaluated the xrays and MRI films independently with discrepancy resolved through consensus. Other variables were identified through detailed chart review of diagnoses and parameters. Forty-five subjects completed one-year followup and were available for analysis. WOMAC and WOMET scores improved significantly in the entire cohort at one year ($p<0.0001$). Patients with

OA grade 0-1 had greater improvements than those with grade 2-3. Mean differences in WOMET and WOMAC scores overall (95% CI, p-value) in 45 subjects at 1 year were 354 (224-483; $p < 0.0001$) and 561 (407-714, $p < 0.0001$); respectively. Subgroup analysis based on lower OA grade (0 and 1) revealed mean differences in WOMET and WOMAC scores of 456 (290-621, $p < 0.0001$) and 656 (466-845, $p < 0.0001$) at 1 year; respectively. Chronicity of symptoms and tear type had no effect on outcomes. Other variables such as age, BMI, type of meniscus tear, smoking history, and psychiatric diagnosis had no significant impact on the results.

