Imaging of muscle cross sectional area: Muscle cross sectional area measurement can provide additional information regarding the functional consequences of meniscectomy. We will image the thigh of patients at enrollment, and at two-year follow up to determine if patients undergoing meniscectomy vs. lavage have greater changes in muscle cross sectional area. Images will be obtained using a rapid axial thigh scan with IDEAL fat/water separation using a 3D spoiled gradient echo sequence. The data will have 1 mm in-plane resolution and 5 mm slice thickness. Acquisition time will be approximately 2 minutes. Muscle cross sectional area will then be determined as previously described {Walton 1997}.

Research Design and Methods

In this study we propose a prospective, randomized, blinded, and controlled clinical trial of arthroscopic meniscectomy in patients between the ages of 45 and 70 with degenerative meniscus tears.

Patient Selection:

Subjects will be recruited from the orthopedic clinic at the VA Palo Alto Healthcare System. Eligible subjects will meet the following inclusion criteria:

1. Age between 45 and 70 years
2. Degenerative meniscus tear as seen by a standard clinical MRI scan
3. A complaint of “mechanical symptoms” which would include popping, catching, or locking of the knee
4. Persistent symptoms for a minimum of three months despite conservative management including anti-inflammatory medications and physical therapy
5. Patient is enrolled for arthroscopic meniscectomy
6. The subject agrees to study follow-up schedule and signs informed consent.

The following exclusion criteria will be enforced:

1. Radiographic osteoarthritis of the knee in any compartment that is greater than KL grade 2
2. Prior knee arthroscopy within two years of study enrollment
3. Unable to have an MRI scan
4. Does not agree to participate

General Study Plan:

Patients who satisfy the inclusion and exclusion criteria and are scheduled for arthroscopic meniscectomy will be approached during their preoperative visit to participate in the study. They will be enrolled when they give informed consent.

Preoperative study related evaluation:

Prior to undergoing surgery, the patient will have the following evaluations:

1. The patient will fill out the WOMET (Kirkley et al., 2007) and WOMAC (Bellamy et al., 1988) surveys.
2. The patient will undergo a gait analysis
3. The patient will have MRI of the knee and thigh.

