Power calculations & bioinformatic analysis. We will test the hypothesis that increased complement activation, cartilage metabolism and/or inflammatory biomarkers are associated with accelerated cartilage loss. We will explore use of (i) predefined indexes of markers of cartilage metabolism (Table 3 above) and markers of inflammation (Table 4 above), and (ii) a combined multivariate test. For the predefined indexes of markers, we will standardize each marker to have standard deviation 1, so an average of 8 independent markers would have a variance 1/8, and an average of 6 a variance of 1/6. For the combined multivariate testing for the cartilage metabolism and the inflammatory markers, we will use 8 and 6 degrees of freedom, respectively, in conjunction with a multivariate Hotelling's T-test. Power calculation: So to achieve an effect (difference in mean index score) of .25 standardized units using a two-sample-test at (0.05 two-sided, power 0.8) would require 29 samples in each group for the 8-marker index, and 43 per group for the 6-marker index.

Statistical Analysis

Randomization:

We will explicitly test if randomization achieved balance between the experimental groups on potentially confounding variables such as age, gender, and body weight. However, confounding may still operate even if the differences between the groups are not statistically significant. Therefore, we will conduct two secondary analyses in which imbalances in important potential confounding variables (duration of symptoms, grade of chondromalacia found on arthroscopic evaluation of the joint, radiographic severity of arthritis (Kellgren-Lawrence), and diagnosis of depression) will be addressed. First, we will simply add these covariates to the primary regression model. However, estimating so many more parameters will inherently reduce the statistical power of the test of the intervention effect. Our second approach solves this problem by first calculating a propensity score (the probability of being in the meniscectomy group based on pre-treatment variables) for each patient, and then using the propensity scores as regression weights in the main regression analysis. This is a state of the art approach for estimating treatment effects in the presence of potential confounding.

Aim 1: *To test the clinical benefit of arthroscopic meniscectomy in the setting of a stable degenerative meniscus tear.*

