Hypothesis 1a: The 12 month WOMAC score will be our primary outcome measure for this aim and the endpoint for this power analysis. The WOMAC is a validated osteoarthritis outcome tool that is widely used to assess the severity of pain, stiffness, and function due to osteoarthritis. A 20% improvement in the total WOMAC score is considered to be clinically important (Kirkley et al., 2008). In a preliminary study, we evaluated a cohort of 45 patients undergoing arthroscopy and meniscectomy at our institution (Mirza et al., 2010). We found a mean preoperative WOMAC score of 1296 with a standard deviation of 392. Twenty percent of the mean baseline score of 1296 is 260.

To ensure patient safety, we are incorporating in our analysis an interim look at the results by the DSMB to ensure that one group does not have dramatically superior results to another group. In addition, the DSMB will assess subject attrition rates by group and adverse events.

This will take place after 25% of the total planned number of subjects complete the study. This analysis will include assessment of drop-out rates and adverse events as well.

Setting the experiment-wide alpha at 0.05 and power at 80%, sample sizes of 37 and 37 achieve 81% power to detect a difference of 260 between the group means with standard deviations of 392 and 392 at a significance level (alpha) of 0.05 using a two-sided independent sample t-test. These results assume that 2 sequential tests are made using the O'Brien-Fleming spending function to determine the test boundaries. The interim look will thus take place when the first 20 subjects (25% of the total 74) complete the 12 month assessment. The analysis assumes that we will stop the trial if either condition is superior. The critical t-value will at the interim look will be +/- 4.3326. If the trial continues, the final analysis will use a critical t-value of 1.96. Sensitivity analyses will be conducted with t-tests on the baseline-to-12-month change scores.

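### Baseline WOMAC is collected but not adjusted for in the primary 12-month comparison: adjusting would be a cheap improvement of uncertain size, not the correction of an error

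*Combined protocol and SAP*

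**What the plan says.** The combined protocol and SAP makes the 12-month WOMAC score the primary outcome of Aim 1. Under Hypothesis 1a, the sample-size statement describes the comparison as made "at a significance level (alpha) of 0.05 using a two-sided independent sample t-test", with 37 patients per arm, a difference of 260, an SD of 392 and 81% power. Hypothesis 1b uses 90% confidence limits for the difference in means, judged against ±194.

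The preoperative evaluation section introduces its list with "Prior to undergoing surgery, the patient will have the following evaluations", and the WOMAC is the first item. In the analysis sections, the baseline score is named only here: "Sensitivity analyses will be conducted with t-tests on the baseline-to-12-month change scores".

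The Randomization part of the Statistical Analysis plans two secondary adjusted analyses. Of the first it says "First, we will simply add these covariates to the primary regression model". The covariates are "duration of symptoms, grade of chondromalacia found on arthroscopic evaluation of the joint", Kellgren-Lawrence grade and a depression diagnosis; baseline WOMAC is not among them. The second uses a propensity score, described as "the probability of being in the meniscectomy group based on pre-treatment variables", with no list of variables. No primary regression model is defined anywhere; Hypothesis 1a describes only a t-test.

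**The concern.** The baseline value of the outcome is an obvious covariate for a 12-month patient-reported score, and here it costs nothing to obtain. The plan itself says that confounding can operate even when group differences are not significant, and it plans adjusted analyses for that reason, but it does not name the baseline outcome among the covariates.

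The two named uses of WOMAC both fix the baseline slope in advance: the raw 12-month comparison sets it to 0 and the change score sets it to 1. No named analysis estimates it. At stake are some precision for 1a and 1b, and an estimate that carries whatever chance baseline imbalance occurs in the one trial that is run. The undefined regression model also leaves it unclear which analysis the secondary covariates are added to.

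**Working it through.** **Inputs from the plan.** 37 per arm, difference 260, SD 392 (the pilot preoperative SD, used for both arms), two-sided alpha 0.05, interim at 20 patients with bound 4.3326, final bound 1.96. The correlation r between baseline and 12-month WOMAC is not given. I assume 0, 0.15, 0.3 and 0.5, with SD 392 at both time points.

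**Plan's own figure.** SE = 392 × √(2/37) = 91.1, and 260/91.1 = 2.85. Normal approximation: 81.4%. Exact t on 72 df: 80.4%. The stated 81% is reproduced.

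**Baseline-adjusted model.** Expected SE = 392 × √[(1 − r²) × (2/37) × (71/70)], on 71 df. The factor 71/70 is the average cost of chance baseline imbalance. **Change score.** SD = 392 × √[2(1 − r)], on 72 df.

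| r | Adjusted SE | Adjusted power | Change-score SD | Change-score power |
|---|---|---|---|---|
| 0 | 91.8 | 79.8% | 554 | 51.2% |
| 0.15 | 90.7 | 80.7% | 511 | 57.9% |
| 0.3 | 87.6 | 83.4% | 464 | 66.2% |
| 0.5 | 79.5 | 89.7% | 392 | 80.4% |

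The unadjusted comparison has SE 91.1 and power 80.4% throughout. The 90% interval for 1b changes in width by essentially the same SE ratio.

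**Break-even, final analysis.** (1 − r²)(71/70) = 1 gives r = √(1/71) = 0.12. The largest loss is at r = 0: 80.4% − 79.8% = about 0.6 points.

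**Break-even, interim.** With 20 patients the factor is 1 + 1/16 = 17/16, so r = √(1/17) = 0.24.

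**What the pilot says about r.** The pilot reports a mean WOMAC difference of 561 (95% CI 407 to 714) in 45 patients, a half-width of 153.5. The methods say only that the scores "were used to evaluate surgical outcome with statistical analysis done by ANOVA", so it is unclear whether the interval is paired.
- If paired: change SD = 153.5/2.015 × √45 = 511, and r = 1 − 511²/(2 × 392²) = 0.15 at equal SDs. With a 12-month SD of 350 instead, r is about 0.06 and adjusting loses slightly (88.3% to 88.0%). With 450, r is about 0.27 and the gain is about 2.6 points.
- If unpaired: the interval says nothing about r.

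**Chance imbalance.** The baseline difference between arms has SE 91.1. A typical imbalance (median absolute value, 0.67 SE, about 61 points) moves the raw 12-month difference by r × 61 = 9, 18 or 31 points at r = 0.15, 0.3 or 0.5. An imbalance at the 95% limit (1.96 × 91.1 = 179 points) moves it by 27, 54 or 89 points. At r = 0.15, power given the typical imbalance is about 78% or 83%, depending on direction. At the 95% limit it is 71% or 88%.

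**The case against.** The strongest reply is that nothing is wrong. The t-test keeps its error rate: in a null simulation at r = 0.3, rejection was 4.9% unadjusted and 5.0% adjusted. The plan already has covariate-adjusted and propensity analyses, and baseline WOMAC may enter the propensity score or the imputation models, whose variables are not listed. The only value of r that can be drawn from the documents, about 0.15, rests on two assumptions and yields 0.3 points of power; a somewhat smaller 12-month SD makes adjustment a slight loss. All of this stands. It limits the point to an inexpensive improvement and rules out any promise of a material gain. The unlisted propensity and imputation variables are missing detail, not part of this point.

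A reader might also infer that the raw and change-score tests would often conflict because baseline imbalance pushes them in opposite directions. In simulation with a true difference of 260, they reach different significance verdicts in about 30%, 27% and 22% of trials at r = 0.15, 0.3 and 0.5. But with baseline means forced equal they still differ in about 20%, 12% and 5%, since the change score has a larger variance at low r and different noise. The adjusted model and the change score also differ in roughly 28%, 21% and 12%. Imbalance alone therefore does not explain the conflict, and adjustment does not remove it.

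**Conclusion.** The point holds as a cheap improvement. The comparison described for 1a and 1b is unadjusted, baseline WOMAC is available, and the one named analysis that uses it has less power than the unadjusted test whenever r is below 0.5 at equal SDs. The reference to an undefined primary regression model is a real ambiguity that the same change would settle.

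The size depends on r, which the documents do not give. At the final look the effect on power runs from a loss of about 0.6 points (r = 0) to a gain of 3.0 points (r = 0.3) or 9.4 points (r = 0.5), assuming 37 completers per arm, SD 392 at both times and a linear baseline effect. The gain may be negligible. What remains is that the linear effect of chance imbalance is taken out of the primary estimate.

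The documents do not support two stronger readings: that the planned t-test is invalid, or that adjustment would bring a large gain in power.

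**What to change.** Before unblinded data are seen, define the primary model as a linear regression of 12-month WOMAC on treatment and baseline WOMAC, fitted in each imputed dataset and combined as the Missing Data section already plans. Use its treatment coefficient for the 1a interim and final tests and for the 1b 90% interval. State that this is the regression model to which the Randomization section adds its covariates. Keep the unadjusted t-test as a sensitivity analysis. Add one sentence saying that the stated critical values apply to the adjusted t statistic.

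**Cost.** No new data, visits or patients. Up to about 0.6 points of power at the final look if r is near 0. At the 20-patient interim the break-even r is higher (about 0.24), but the strict bound makes this of little practical effect. The critical values barely change meaning: 4.3326 has a nominal two-sided p of 0.00045 on 17 df against 0.00040 on 18 df, and 1.96 has p = 0.0539 on either 71 or 72 df. Because the estimators for 1a and 1b are replaced, the timing of the change must be documented.

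### The interim and final critical t-values (4.3326 and 1.96) are normal-scale boundaries; applied to t statistics on 18 and 72 df they give a type I error of about 5.4%, not 5%

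*Combined protocol and SAP*

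**What the plan says.** All of the following is in Statistical Analysis, Aim 1, Hypothesis 1a.

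- Error rate and target power: "Setting the experiment-wide alpha at 0.05 and power at 80" (per cent).
- Test: "at a significance level (alpha) of 0.05 using a two-sided independent sample t-test".
- Size and power: "sample sizes of 37 and 37 achieve 81% power", calculated for a 260-point gap and an SD of 392 in each arm.
- Looks: two, with boundaries from an O'Brien-Fleming spending function. The trial stops if either arm is superior, so crossing the interim boundary counts as a rejection.
- Interim timing: "The interim look will thus take place when the first 20 subjects (25% of the total 74) complete the 12 month assessment".
- Interim boundary: "The critical t-value will at the interim look will be +/- 4.3326".
- Final boundary: "If the trial continues, the final analysis will use a critical t-value of 1.96".

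Nothing in the Statistical Analysis section says that the two cut-offs are on the normal scale, or that they will be turned into nominal p-values before use.

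**The concern.** A spending function allots probability. The matching cut-off depends on the reference distribution of the statistic. A t statistic has heavier tails than a normal one, so a normal cut-off applied to it rejects too often. The effect is slight at 72 df and large in relative terms far out in the tail at 18 df.

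As written, the named test, the stated alpha and the stated cut-offs cannot all hold. The rule decides the primary outcome. If the final |t| falls between 1.960 and 1.993, the written rule declares significance while the t-test itself reports p above 0.05, so one prespecified test gives two opposite answers. The same result also decides whether Hypothesis 1b is tested at all, because the non-inferiority comparison is made only if no difference is found.

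**Working it through.** **Inputs** (Hypothesis 1a): alpha 0.05 two-sided; 37 + 37 subjects, so 72 df at the end; 20 completers at the interim, so 18 df; difference 260; SD 392 per arm; cut-offs 4.3326 and 1.96. The 10 v 10 split at the interim follows from the permuted blocks of 10 described under the evaluation at the time of surgery.

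**1. Reproduce the plan's boundaries.** O'Brien-Fleming-type spending with 0.025 per side at information fraction f spends 2 × [2 − 2Φ(z₀.₉₈₇₅/√f)] by the interim look.

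- At f = 0.25: z₀.₉₈₇₅ = 2.2414; 2.2414/0.5 = 4.4828; alpha spent = 0.0000147. The two-sided normal cut-off for that amount is 4.3326.
- Solving the bivariate normal with correlation √0.25 = 0.5 for a total of 0.05 gives a final cut-off of 1.9600.

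Both match the plan to every printed digit, and for normal statistics they give a total alpha of 0.0500. They are therefore normal-scale values.

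**2. Reproduce the plan's power.** SE = 392 × √(2/37) = 91.14; 260/91.14 = 2.853; Φ(2.853 − 1.96) = 0.814. This agrees with the stated 81%.

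**3. Apply the cut-offs to t statistics, as written.**

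| Look | df | Cut-off | Two-sided null probability on the t scale | On the normal scale | Cut-off with the same p-value on the t scale |
|---|---|---|---|---|---|
| Interim | 18 | 4.3326 | 0.00040 | 0.0000147 | 5.87 |
| Final | 72 | 1.96 | 0.0539 | 0.0500 | 1.9935 |

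The interim probability is 0.00040/0.0000147, or about 27 times the allotted amount. In absolute terms it is only 0.04 percentage points.

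**4. Both looks together.** The two probabilities sum to at most 0.0539 + 0.0004 = 0.0543. A simulation of 3,000,000 null trials (pooled t-tests at 10 + 10 and then 37 + 37) gives 0.0540, with a Monte Carlo standard error of about 0.013 percentage points. With cut-offs 5.87 and 1.9935 the same simulation gives 0.0500.

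**5. Power with a t threshold.** From the noncentral t distribution with noncentrality 2.853 and 72 df, power is 81.3% at 1.96 and 80.4% at 1.9935.

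**6. Interim fraction.** 20/74 = 0.270, whereas 0.25 × 74 = 18.5. At f = 20/74 the spending function allots 0.0000324, which is z = 4.156, or |t| = 5.49 on 18 df. The final normal cut-off stays at 1.960. The printed 4.3326 thus belongs to a different fraction from the planned look.

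**The case against.** **The effect is small.** In WOMAC units the final threshold moves from 1.96 × 91.14 = 178.6 to 1.9935 × 91.14 = 181.7 points, about 3 points against a target of 260. The chance of landing between the two cut-offs is about 0.4% under the null (0.0539 − 0.0500) and 0.9% under the design alternative (81.3% − 80.4%). This stands, and it limits the importance of the point.

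**The authors probably meant z boundaries.** The paragraph already sets alpha at 0.05 for a two-sided t-test, so an analyst who reads the p-value from the software would be right at the end of the trial. That is a likely reading of the intent. But the text prescribes a comparison of t with 1.96, and no sentence overrides it.

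**The 72 df are not certain.** The Missing Data paragraph puts all analyses on the intent-to-treat sample with ten imputed datasets, and 82 subjects are to be enrolled. With 80 nominal df the probability beyond 1.96 is 5.35%. With pooled imputation df it cannot be fixed in advance. This qualifies the exact figure, and it is also a reason not to hard-code a cut-off.

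**The 27% slip does not inflate alpha.** This is correct: on the normal scale 4.3326 is stricter than the 4.156 that belongs to 20/74. Twenty is also the multiple of the block size nearest to 18.5. It remains a mismatch between boundary and look, but no part of the 5.4% comes from it.

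**The stated 81% fits the written rule.** This also stands: it falls to 80.4% only when the threshold is corrected.

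**Conclusion.** The concern holds. The two cut-offs are normal-scale boundaries labelled and used as t-values, and applied literally they give an overall type I error of about 5.4% against the stated 5%. Nearly all of the excess of 0.4 percentage points comes from the final 1.96; the interim look adds at most 0.04 points. The figure assumes normal data, equal variances, complete data on 37 per arm and a 10 v 10 interim look. The planned imputation would change it somewhat. The error is modest, but it lies in the primary decision threshold and costs almost nothing to correct, so it should be corrected.

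**What to change.** In Hypothesis 1a, replace the two cut-off sentences with nominal two-sided p-values taken from the t distribution of the model actually fitted:

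- **Final analysis:** p < 0.05, which is |t| > 1.993 at 72 df, or the corresponding value at the pooled df when imputed datasets are combined.
- **Interim look:** the p-value that the spending function gives at the fraction actually observed. This is 0.0000324 at 20 of 74 (|t| > 5.49 at 18 df), or 0.0000147 if the look is held at 25%.

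Correct either the 25% or the count of 20 so that they agree, and restate power as 80% (80.4%).

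The cost is a few sentences and about one point of stated power. The sample size of 74 completers still meets the 80% target.

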74 subjects will thus be needed to complete the trial. Over a one year period we will expect to have a 10% lost to follow-up rate. We will thus plan to enroll 82 subjects into the study. With a 70% recruitment rate we will need to have 117 candidate patients for this study. In calendar year 2011, we performed 66 arthroscopic meniscectomies at our facility. Assuming that 70% of these cases involved stable degenerative tears, we would have 46 candidate patients per year. It would thus take us approximately 2.5 years to recruit enough patients for the study if we were to operate at last year's rate. We presently have approximately 100 patients for knee arthroscopy on our waiting list for surgery, which makes it likely that we could accomplish this goal more rapidly.

Hypothesis 1b: Should we fail to find a difference in 12 month WOMAC scores, we will test the hypothesis that the WOMAC scores in the arthroscopy and lavage condition are at least as good as (non-inferiority) the meniscectomy by setting "d" the largest difference in WOMAC scores which we consider to be clinically meaningless to 15% of baseline, or 194 points. We will then calculate 90% confidence limits for the difference in means for the two groups and determine whether these confidence limits lie within the -194 to 194 point interval. Since there is no danger to patients if this hypothesis is found to be true, this hypothesis will not be subject to an interim analysis. We will assume that the standard deviation of the means is 392. With these numbers, the sample size of 74 and alpha = .10 and yields power = .80.

Aim 2: *To test the functional effect of arthroscopic meniscectomy in the setting of a degenerative meniscus tear.*

Hypothesis 2: Subjects randomized to arthroscopy and meniscectomy will have greater changes in tibio-femoral rotation, knee adduction moment, and knee flexion moment at 12 months following surgery when compared to subjects randomized to arthroscopy and lavage.

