Calculations were performed to estimate the necessary sample size for the endpoints of Aim 2 of changes in tibio-femoral rotation, knee adduction moment, and knee flexion moment. In order to keep the family-wise error rate at .05, each comparison will be made with an independent sample t-test with alpha = 0.0167. To reject the null hypothesis that changes in tibio-femoral rotation will not differ between the intervention (meniscectomized) knees and control (non-meniscectomized knees), data from a similar study performed in our laboratory evaluating tibial rotation using the same techniques between meniscectomized knees and intact knees was used (Netravali et al., 2010). In that study, we found a 3.2 degree difference in tibio-femoral rotation in meniscectomized knees when compared to intact contralateral knees using a t-test. The standard deviation of the measurements in the meniscectomized knees was 3.8 degrees. Thus, to detect a difference of 3.2 degrees tibio-femoral rotation in the meniscectomized group

versus no change in the intact group, with an alpha of 0.0167 and 74 total patients, power of 87% will be achieved.

In addition, we would be interested to detect a change in peak adduction moment of about 10% of baseline value. This corresponds to a change of 0.35%BW*ht (Netravali et al., 2010). Prior work looking at changes in knee adduction moment with intervention find a standard deviation of the difference in peak adduction moment with the intervention to be 0.35%BW*ht. With an alpha of 0.0167 and 74 total patients, power of 94% will be achieved.

Finally, we are interested in detecting a change in peak flexion moment of about 10% baseline value. This corresponds to a change of 0.3%BW*ht (Netravali et al., 2010). Assuming a standard deviation of the flexion moment of approximately 0.35%BW*ht. With an alpha of 0.0167 and 74 total patients, power of 89% will be achieved.

Missing Data:

All analyses will be on the intent-to-treat sample. To address missing data at 1 year (and other time points), we will use a multiple imputation strategy that minimizes potential attrition bias. Ten datasets will be imputed with draws from the theoretical complete data distribution using the Multivariate Imputation by Chained Equations (MICE) program implemented in the R statistical language. All analyses with these data will be conducted on the imputed datasets and combined to yield the final parameter estimates and inferences.

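### Hypothesis 1b: the stated power of .80 belongs to a one-sided 10% non-inferiority test; the written rule (both 90% limits within ±194) has about 36% power at a true difference of 0

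*Combined protocol and SAP*

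**What the plan says.** The point concerns one paragraph, Hypothesis 1b under Aim 1 in the Statistical Analysis section. It applies if Hypothesis 1a finds no difference in 12-month WOMAC.

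- **Hypothesis.** Lavage scores "are at least as good as (non-inferiority) the meniscectomy".
- **Margin.** The largest difference regarded as "clinically meaningless to 15% of baseline, or 194 points".
- **Rule.** "We will then calculate 90% confidence limits for the difference in means for the two groups", and then "determine whether these confidence limits lie within the -194 to 194 point interval".
- **Variability.** "We will assume that the standard deviation of the means is 392".
- **Power.** "With these numbers, the sample size of 74 and alpha = .10 and yields power = .80".

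The paragraph does not say whether the alpha of .10 is one-sided or two-sided, and it gives no assumed true difference. Hypothesis 1a sets the allocation at 37 and 37 and fixes the final cut-off: "If the trial continues, the final analysis will use a critical t-value of 1.96".

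**The concern.** The hypothesis, the rule and the power statement do not describe the same test. Non-inferiority looks in one direction. Requiring both limits to lie inside a symmetric interval is equivalence, that is, two one-sided tests at 5% each when the interval is 90%. An alpha of .10 with power of .80 fits neither a 90% interval used on one side nor one used on both.

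If 1a is null, 1b is the planned route to a positive statement that lavage is as good as meniscectomy. An overstated power hides how likely an inconclusive answer is. A label and a rule that disagree also leave room to choose the reading after the data are seen. A non-significant result in favour of lavage could fail a test of whether lavage is at least as good.

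**Working it through.** **Inputs.** Margin 194 (15% of the baseline mean: 0.15 × 1296 = 194.4). SD 392, taken as the SD of individual scores, as in Hypothesis 1a. 37 per arm, so 72 degrees of freedom. The true difference is not stated; 0 is assumed because it is the most favourable value for the written rule.

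**Standard error.** SE = 392 × √(2/37) = 91.14, and 194 / 91.14 = 2.129.

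**Reproducing the stated .80.** One-sided non-inferiority at 10%, normal approximation: Φ(2.129 − 1.282) = 0.802. By noncentral t: 0.798. This matches. It corresponds to one limit of an 80% interval.

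**The written rule.** Both 90% limits inside ±194, normal approximation: 2 × Φ(2.129 − 1.645) − 1 = 0.371. By t, integrating over the estimated SD: 0.357.

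**All four combinations** (37 per arm, true difference 0):

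| Interval | Limits used | Power (t) | Power (normal) |
|---|---|---|---|
| 90% | both (as written) | 0.357 | 0.371 |
| 90% | one | 0.679 | 0.686 |
| 80% | both | 0.596 | 0.603 |
| 80% | one | 0.798 | 0.802 |

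**What the written rule demands.** The 90% half-width is 1.666 × 91.14 = 151.9. At an observed SD of 392, the rule passes only if the observed difference is within ±(194 − 151.9) = ±42.1. Hypothesis 1a is non-significant up to 1.96 × 91.14 = 178.6. So a non-significant result favouring lavage by roughly 43 to 179 points fails 1b.

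**Simulation.** In 4 million equal-arm trials with the SD estimated in each and the 1.96 cut-off for 1a:

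- 1a significant: 5.4%
- both 90% limits inside ±194: about 36%
- neither: about 59%
- 1a non-significant and the 90% limit on the side where lavage is worse clears 194, yet the written rule fails: about 29%

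**Sensitivity (by t).**

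- Lavage truly worse by 50 points: 0.31 (90%, both limits), 0.47 (90%, one), 0.61 (80%, one).
- 41 per arm, an upper bound if imputation recovered full information on all 82 enrolled: 0.44 (90%, both), 0.72 (90%, one).
- SD varied, 90% both limits: 0.73 at 300, 0.57 at 340, 0.16 at 450. The rule reaches 0.80 only at an SD of about 283.
- For context, 80% power with a 90% interval needs 52 per arm (one limit) or 71 per arm (both limits).

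**The case against.** The strongest reply is that the paragraph gives one explicit rule that can be carried out as it stands. A margin defined as a clinically meaningless difference is symmetric, and the test follows a failure to find a difference; both suggest equivalence was meant. On that view only the label and the power figure need changing, and using one limit lowers the bar. This has force: the documents do not settle the intent, so keeping the written rule under its proper name is a legitimate choice. It does not rescue the stated power, which is then about 36%.

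The 29% should be read for what it is. It compares the written rule with one particular reading of the label (one 90% limit). The plan does not itself produce two results.

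The 36% depends on an SD of 392, which is a preoperative value reused at 12 months, and a smaller SD would raise it. But 392 is the plan's own input, and the .80 was obtained with it. Reading 74 as per arm gives 0.82 for the written rule and contradicts the 37 and 37 in Hypothesis 1a. The Missing Data section says "All analyses will be on the intent-to-treat sample" and plans multiple imputation, but even full recovery of all 82 leaves both 90% readings short of .80.

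Finally, 1b is conditional, the sample size was set by 1a, and the written rule errs on the strict side. That limits the harm to an overstated power and an ambiguous criterion. It does not remove either.

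**Conclusion.** The concern holds. The power of .80 is correct for a one-sided 10% non-inferiority test and wrong for the rule the plan prescribes. On the plan's SD of 392, with 37 per arm and an assumed true difference of 0, the written rule has power of about 0.36; a true difference in either direction would lower it. Using one limit of the 90% interval gives about 0.68, so the stated figure fits a 90% interval on neither reading. The SD must also be read as that of individual scores: taken literally as an SD of means, 392 exceeds the margin and power near .80 would be impossible.

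This must be fixed before unblinding, because it sets the criterion for interpreting a null primary result. Hypothesis 1a, enrolment and the interim look are not affected.

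**What to change.** Keep 74 completers. Before any unblinded comparison of 12-month scores, state together the hypothesis type, the one-sided alpha, the interval level and the assumed true difference, and give the power of that combination.

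**Recommended, because it matches the named hypothesis:** *If Hypothesis 1a is not significant, lavage is declared non-inferior if the 90% confidence limit on the side where lavage is worse is less than 194 points (one-sided alpha 0.05); the other limit is not used. With an SD of individual scores of 392, 37 per arm and a true difference of 0, power is about 68%.*

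**Alternatives that are also internally consistent:**

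- If two-sided equivalence with a 90% interval is intended, keep the rule, rename the hypothesis and state power of about 36%.
- If one-sided alpha 0.10 is intended, say so and use an 80% interval (power 0.80 with one limit, 0.60 with both). This accepts a 10% chance of a false claim at the margin and would have to be reconciled with the experiment-wide alpha of 0.05 in Hypothesis 1a.

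In every case, replace the phrase about the standard deviation of the means with the SD of individual scores.

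The cost is SAP wording only, with no extra patients, visits or data. The stated power falls to about 68% or 36% unless one-sided alpha 0.10 is openly adopted.
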